**Table 8-1 Etoposide and Carboplatin Dose Reductions**

Dose level	Etoposide (mg/m  )	Carboplatin (AUC)
Dose level -1 (first dose reduction)	Reduce to 75 mg/m 	Reduce to AUC = 4
Dose level -2 (second dose reduction)	Reduce to 50 mg/m 	Reduce to AUC = 3

AUC = area under the concentration-time curve

### Dose Modifications for Hematologic Toxicity

#### First Day of Induction Cycle 2 and Beyond

In order to start Induction Cycle 2 and subsequent induction cycles as scheduled, on Day 1 of the cycle, patients must have an ANC  $\geq 1.5 \times 10^9/L$ , platelet count  $\geq 100 \times 10^9/L$ , and nonhematologic drug-related toxicities (except alopecia) must be  $\leq$  Grade 1 or have returned to baseline. The dose adjustments in [Table 8-2](#) are based on the ANC and platelet counts on the first day of treatment for Cycle 2 and each subsequent induction cycle.

**Table 8-2 Etoposide and Carboplatin Dose Adjustments Based on Lack of Recovery of Absolute Neutrophil or Platelet Counts on the First Day of Induction Cycle 2 and Each Successive Cycle**

Absolute Neutrophil Count <math>< 1.5 \times 10^9/L</math>	Etoposide	Carboplatin
First episode	No change. Use G-CSF with subsequent cycles. Refer to the American Society of Clinical Oncology (ASCO) guidelines (Smith 2015).	No change. Use G-CSF with subsequent cycles. Refer to ASCO guidelines (Smith 2015).
Second episode	First dose reduction	First dose reduction
Third episode	Second dose reduction	Second dose reduction
Fourth episode	Discontinue drug	Discontinue drug
Platelet Count <math>< 100 \times 10^9/L</math>	Etoposide	Carboplatin
First episode	First dose reduction	First dose reduction
Second episode	Second dose reduction	Second dose reduction
Third episode	Discontinue drug	Discontinue drug

G-CSF = granulocyte colony-stimulating factor

### Neutrophils

The dose adjustments in [Table 8-3](#) are based on the ANC nadir with or without fever during the preceding treatment cycle.

**Table 8-3 Etoposide and Carboplatin Dose Adjustments Based on Absolute Neutrophil Count Nadir With or Without Fever**

ANC Nadir	Etoposide	Carboplatin
Grade 3a (without fever)	No Change	No change
Grade 4b for ≥ 7 days (without fever)		
First episode	No change. Use G-CSF with subsequent cycles. Refer to the ASCO guidelines (Smith 2015).	No change. Use G-CSF with subsequent cycles. Refer to ASCO guidelines (Smith 2015).
Second episode	First dose reduction	First dose reduction
Third episode	Second dose reduction	Second dose reduction
Fourth episode	Discontinue drug	Discontinue drug
Grade 3/4 with fever		
First episode	No change. Use G-CSF with subsequent cycles. Refer to the ASCO guidelines (Smith 2015).	No change. Use G-CSF with subsequent cycles. Refer to ASCO guidelines (Smith 2015).
Second episode	First dose reduction	First dose reduction
Third episode	Second dose reduction	Second dose reduction
Fourth episode	Discontinue drug	Discontinue drug

ANC = absolute neutrophil count; G-CSF = granulocyte colony-stimulating factor

a Grade 3 ANC: 500 to < 1000/mm^3

b Grade 4 ANC: < 500/mm^3

Platelets

The dose adjustments in [Table 8-4](#) are based on the platelet nadir during the preceding treatment cycle.

**Table 8-4 Etoposide and Carboplatin Dose Adjustment Based on Platelet Nadir**

Platelet Count Nadir	Etoposide	Carboplatin
Grade 4a or ≥ Grade 3b with bleeding		
First episode	First dose reduction	First dose reduction
Second episode	Second dose reduction	Second dose reduction
Third episode	Discontinue drug	Discontinue drug

a Grade 4 platelet count: <25,000/mm^3

b Grade 3 platelet count: 25,000 to < 50,000/mm^3

### Colony Stimulating Factors

**Patients will not receive colony stimulating factors (CSFs; eg, granulocyte colony stimulating factor [G-CSF]; granulocyte-macrophage colony-stimulating factor [GM-CSF]) or erythropoiesis stimulating agents (ESAs) during Induction Cycle 1 (ie, prior to the actual Cycle 2 Day 1 dosing visit).**

Although CSFs should not be routinely used as adjunctive treatment with antibiotic therapy for patients with fever and neutropenia in any cycle, they may be considered in patients with fever and neutropenia who are at high risk for infection-associated complications or who have prognostic factors predictive of poor clinical outcomes (including in Induction Cycle 1 if necessary). Subsequent use **after Induction Cycle 1** will be based on toxicities as outlined above. Please also refer to the ASCO guidelines ([Smith 2015](#)) for neutropenia.

When indicated, as outlined above in [Table 8-2](#) and [Table 8-3](#), either filgrastim or pegfilgrastim may be used per the prescribing information. In the event a patient has a neutropenic event requiring G-CSF in the subsequent cycle, then filgrastim or pegfilgrastim should not be initiated until at least 24 hours after dosing of the next subsequent cycle is complete (ie, no earlier than Day 4 of the next subsequent cycle). Filgrastim or pegfilgrastim should not be used to increase low neutrophil counts mid-cycle or prior to the start of the subsequent cycle.

For a hemoglobin level < 9.0 g/dL or symptomatic anemia when indicated, epoetin alfa or darbepoetin alfa may be used to treat patients per the prescribing information.

#### 8.4.5.2.1. Dose Modifications for Nonhematologic Toxicity

### Hepatic Toxicity

The following dose adjustments for etoposide and carboplatin are based on serum AST/ALT and bilirubin levels ([Table 8-5](#)) during the preceding treatment cycle.

**Table 8-5 Etoposide and Carboplatin Reduction for Hepatic Toxicity**

AST/ALT		Bilirubin	Etoposide	Carboplatin
Grade 1	and/ or	≤ Grade 2	No change	No change
≥ Grade 2	and/or	≥ Grade 3		
First episode		First episode	First dose reduction	First dose reduction
Second episode		Second episode	Second dose reduction	Second dose reduction
Third episode		Third episode	Discontinue drug	Discontinue drug

For patients enrolled with baseline AST and ALT  $\geq 3 \times$  ULN in the presence of liver metastases, if further increase in AST and ALT occurs, trilaciclib or placebo + E/P should be held until the patient is discussed with the medical monitor.

Gastrointestinal toxicity

Nausea and vomiting should be managed with the use of adequate antiemetic therapy. Prophylactic anti-emetic therapy can be used at the discretion of the treating physician. Dexamethasone should be avoided as an antiemetic, if possible. Patients are encouraged to take plenty of oral fluids.

Diarrhea should be managed with appropriate antidiarrheal therapy. Patients should be encouraged to take plenty of oral fluids.

Hypersensitivity Reactions

For patients who had a mild to moderate hypersensitivity reaction and have been successfully re-challenged, careful attention to prophylaxis and bedside monitoring of vital signs is recommended for all subsequent doses.

Mild symptoms (eg, mild flushing, rash, pruritus): complete infusion. Supervise at bedside. No treatment required.

Moderate symptoms (eg, moderate rash, flushing, mild dyspnea, chest discomfort): stop infusion. Give IV diphenhydramine 25 mg and IV dexamethasone 10 mg. Resume infusion after recovery of symptoms at a low rate, 20 mg/hour. If no further symptoms occur after 15 minutes, the rate may be increased to the full rate until the infusion is complete. If symptoms recur, the infusion must be stopped. The patient should receive no additional etoposide or carboplatin for that cycle, but may receive additional doses at the discretion of the investigator.

Severe life-threatening symptoms (eg, hypotension requiring vasopressor therapy, angioedema, respiratory distress requiring bronchodilation therapy, generalized urticarial): stop infusion immediately. Give IV diphenhydramine and dexamethasone as above. Add epinephrine or bronchodilators if indicated. If wheezing is present, that is not responsive to bronchodilators, epinephrine is recommended. Patient should not receive any further doses of etoposide or carboplatin. Report this occurrence as an AE.

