**Table 5-1 G1T28-05: Study Objectives and Endpoints**

PRIMARY OBJECTIVES	PRIMARY ENDPOINTS	
Evaluate potential of trilaciclib, compared with placebo, to reduce chemotherapy-induced myelosuppression in patients with SCLC undergoing treatment with E/P/A	All Regions	
	
 
• Duration of severe (Grade 4) neutropenia in Cycle 1
 
• Occurrence of severe (Grade 4) neutropenia
 
	
KEY SECONDARY OBJECTIVES	KEY SECONDARY ENDPOINTS	
Evaluate potential of trilaciclib, compared with placebo, to reduce chemotherapy-induced myelosuppression and its consequences in patients with SCLC undergoing treatment with E/P/A	Region 1	Region 2
	
 
• Occurrence of RBC transfusions on/after Week 5 (proportion of patients)
 
• Occurrence of G-CSF administration (proportion of patients)
 
• A composite endpoint (MAHE; number of events for all components) defined to include:                             
 
• All-cause hospitalizations
 
• All-cause dose reductions
 
• Febrile neutropenia
 
• RBC transfusions on/after Week 5
 
• Prolonged severe (Grade 4) neutropenia (duration > 5 days)
 
 
 
	
 
• Overall survival (will not be factored into multiplicity adjustment)
 
• All-cause dose reductions (number of events)
 
• Occurrence of RBC transfusions on/after Week 5 (proportion of patients)
 
• Occurrence of G-CSF administration (proportion of patients)
 

SUPPORTIVE SECONDARY OBJECTIVES	SUPPORTIVE SECONDARY ENDPOINTS	
Evaluate potential of trilaciclib, compared with placebo, to reduce chemotherapy-induced myelosuppression and its consequences in patients with SCLC undergoing treatment with E/P/A	All Regions	
	
 
• (Region 1 ONLY) OS (analysis will focus on “do no harm”)
 
• (Region 2 ONLY) A composite endpoint (MAHE; number of events for all components) defined to include:                             
 
• All-cause hospitalizations
 
• All-cause dose reductions
 
• Febrile neutropenia
 
• RBC transfusions on/after Week 5
 
• Prolonged severe neutropenia (duration > 5 days)
 
 
 
	

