#### 7.1.1. Inclusion Criteria

For a patient to be eligible for participation in this study, *all* of the following criteria must apply.

1. Age  $\geq$  18 years
2. Unequivocally confirmed diagnosis of SCLC by histology or cytology, preferably including the presence of neuroendocrine features by immunohistochemistry
3. Extensive-stage SCLC
4. At least 1 target lesion that is measurable by RECIST v1.1 ([Eisenhauer 2009](#))
5. Hemoglobin  $\geq$  9.0 g/dL
6. Absolute neutrophil count (ANC)  $\geq$   $1.5 \times 10^9$ /L
7. Platelet count  $\geq$   $100 \times 10^9$ /L
8. Creatinine  $\leq$  1.5 mg/dL or glomerular filtration rate (GFR) of  $\geq$  60 mL/minute
9. Total bilirubin  $\leq$   $1.5 \times$  ULN;  $< 3 \times$  ULN if the patient has documented Gilbert's disease
10. AST and ALT  $\leq$   $2.5 \times$  ULN;  $\leq 5 \times$  ULN in the presence of liver metastases
11. ECOG performance status of 0 to 2
12. Predicted life expectancy of  $\geq$  3 months
13. Contraception:
  - a. For females: All females of childbearing potential must have a negative serum beta human chorionic gonadotropin ( $\beta$ -hCG) test result at screening. Females must be either postmenopausal, surgically sterile, or agree to use 2 forms of highly effective contraception during the study and for 6 months following discontinuation of study treatment

- i. Postmenopausal is defined as (1) at least 60 years of age, (2) medically confirmed ovarian failure, or (3) younger than 60 years of age and have had cessation of regular menses for at least 12 consecutive months with no alternative pathological or physiological cause and/or serum levels of estradiol and follicle stimulating hormone within the laboratory's reference range for postmenopausal females
- ii. Acceptable surgical sterilization techniques are complete or partial hysterectomy, bilateral tubal ligation with surgery at least 6 months prior to dosing, or bilateral oophorectomy with surgery at least 2 months prior to dosing
- iii. Highly effective methods of contraception are those that result in a low failure rate (ie, less than 1% per year) when used consistently and correctly. These include the following:
  1. Established use of oral, injected or implanted hormonal methods of contraception (stable dose at least 3 months prior to dosing)
  2. Placement of an intrauterine device or intrauterine system

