### Other Toxicities

For the first occurrence of any nonhematologic Grade 2 chemotherapy-related toxicity (except alopecia), trilaciclib or placebo + E/P should be withheld until the toxicity recovers to Grade 1 or baseline. Treatment may then be resumed at the same dose level. For the second occurrence of any nonhematologic Grade 2 chemotherapy-related toxicity (except alopecia), following recovery of the toxicity to Grade 1 or baseline, E/P should be resumed at dose level -1; for the third occurrence, the E/P doses should be reduced to dose level -2. A fourth occurrence will result in discontinuation of trilaciclib or placebo + E/P therapy. No dose reduction should be made for Grade 1 toxicities.

For any Grade 3 or 4 chemotherapy-related toxicities not mentioned above, trilaciclib or placebo + E/P should be withheld until the toxicity recovers to Grade 1 or baseline. Treatment should then be resumed at dose level -1 for the first occurrence and dose level -2 for the second occurrence. A third occurrence will result in discontinuation of trilaciclib or placebo + E/P therapy.

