6.2.7.1.2 Key Secondary Efficacy Analyses

Occurrence of RBC transfusions on/after 5 weeks on study is a binary variable and will be summarized using the same method for occurrence of SVN described in [Section 6.2.7.1.1](#) except baseline HGB will be used as a covariate instead of baseline ANC in the modified Poisson model. Also, the offset will be the logarithm transformation of duration of induction treatment period divided by 7 (i.e. week) instead of number of induction cycles, and. An additional sensitivity analysis will look all transfusions during the induction treatment period, and all transfusions with a subset of subjects completing at least 1 cycle.

Occurrence of GCSF administration is a binary variable and will be summarized using the same method for occurrence of SVN described in [Section 6.2.7.1.1](#).

All-cause dose reductions will be analyzed to compare trilaciclib and placebo using a negative binomial regression model to account for the potential over-dispersion. The model includes the stratification factors of ECOG (0 or 1 vs. 2) and brain metastases (Yes vs. No), and treatment as a fixed effect. The logarithm transformation of number of induction cycles will be included as an offset variable in the modeling. The two-sided p-value, aRR (trilaciclib vs placebo) and its 95% CIs will be presented.

The total number of all-cause dose reductions will be summarized descriptively, along with the number of induction cycles, and the event rate per cycle (calculated as the total number of events/total number of induction cycles). The cumulative incidence of events during the induction treatment period will be summarized and presented graphically by cycle.

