6.2.7.1.4 Multiplicity Adjustments

The clinical trial evaluates the objectives defined in terms of the comparison of trilaciclib + E/P/A versus placebo + E/P/A on the primary and key secondary myelosuppression efficacy endpoints in [Sections 5.1.1 and 5.1.2](#).

The multiplicity problem includes the following 5 hypotheses of no effect:

- Hypothesis H_1 . Comparison of trilaciclib + E/P/A versus placebo + E/P/A for duration of severe (Grade 4) neutropenia in Cycle 1.
- Hypothesis H_2 . Comparison of trilaciclib + E/P/A versus placebo + E/P/A for occurrence of severe (Grade 4) neutropenia.
- Hypothesis H_3 . Comparison of trilaciclib + E/P/A versus placebo + E/P/A for all-cause dose reductions in the MAHE composite.
- Hypothesis H_4 . Comparison of trilaciclib + E/P/A versus placebo + E/P/A for occurrence of RBC transfusions on/after Week 5 on study.
- Hypothesis H_5 . Comparison of trilaciclib + E/P/A versus placebo + E/P/A for occurrence of G-CSF administration.

These 5 hypotheses can be grouped into 3 families:

- Family 1 (F_1) includes the hypothesis H_1 .
- Family 2 (F_2) includes the hypothesis H_2 .
- Family 3 (F_3) includes the hypotheses H_3 , H_4 , and H_5 .

[figure not shown]
The 1-sided p-values for these 5 comparisons will be used for the multiple testing procedure.

A Hochberg-based gatekeeping procedure will be utilized to control the global familywise error rate across the 5 null hypotheses in the strong sense at a 1-sided $\alpha=0.025$ level, and it satisfies the positive dependence condition at the 1-sided setting. The procedure is built using the mixture methodology developed in Dmitrienko and Tamhane (2011) and accounts for the logical restrictions among the 5 hypotheses displayed in

Figure 2 by performing multiplicity adjustments in three steps. The logical restrictions can be achieved by defining the parallel set and serial set for each individual hypothesis based the tree-structured procedure introduced by Dmitrienko et al (2007).

- Step 1. The trilaciclib vs placebo comparisons for Family 1 (hypothesis H_1) are performed using a truncated version of the Hochberg procedure. The truncation parameter γ is set to 0.
- Step 2. The trilaciclib vs placebo comparisons for Family 2 (hypothesis H_2) are performed using a truncated version of the Hochberg procedure if H_1 is significant in Step 1. The truncation parameter γ is set to 0.

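### The hepatic rules for etoposide and carboplatin give more than one instruction for the same AST/ALT and bilirubin result, so one new Grade 2 episode can yield 0 or 1 event in the dose-reduction endpoint

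*Protocol*

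**What the plan says.** Protocol 8.4.5.2.1 (Hepatic Toxicity) states that "dose adjustments for etoposide and carboplatin are based on serum AST/ALT and bilirubin levels" during the preceding cycle. The table it points to, "Etoposide and Carboplatin Reduction for Hepatic Toxicity", has two rows:

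- **No change:** AST/ALT Grade 1 and/or bilirubin up to Grade 2.
- **Reduction:** AST/ALT Grade 2 or higher and/or bilirubin Grade 3 or higher. The first episode brings the first reduction, the second episode the second reduction, and the third discontinuation.

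A sentence below the table covers patients with liver metastases whose baseline AST and ALT were at least 3 x ULN: "if further increase in AST and ALT occurs, trilaciclib or placebo + E/P should be held" until the case is discussed with the medical monitor.

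Later in 8.4.5.2.1, Other Toxicities begins its Grade 2 rule "For the first occurrence of any nonhematologic Grade 2 chemotherapy-related toxicity (except alopecia". Under that rule E/P is withheld until recovery and may resume at the same dose. The second occurrence leads to level -1, the third to level -2, and the fourth to discontinuation.

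Protocol 8.4.5.2, which introduces all of these rules, ties adjustments to drug-related toxicity and allows at most two reductions per patient. Inclusion criterion 10 admits AST/ALT up to 5 x "ULN in the presence of liver metastases". SAP Table A-1 grades AST and ALT above 3.0 and up to 5.0 x ULN as Grade 2.

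On the endpoint, SAP 6.2.7.1.2 states that "All-cause dose reductions will be analyzed to compare trilaciclib and placebo", by negative binomial regression with the log number of induction cycles as offset. H3 in SAP 6.2.7.1.4 is the comparison "for all-cause dose reductions in the MAHE composite".

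**The concern.** A dosing table should send each laboratory result to one action. This one does not, and a neighbouring rule in the same section gives a different action for what may be the same event. Protocol 7.1 plans up to 60 centres for about 100 patients, so many sites will treat only one or two patients and will settle the question separately.

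Two things are at stake. The chemotherapy given could differ between identical patients. Those differences would also pass into a low count, capped at two per patient. That count is a Region 2 key secondary endpoint, a MAHE component, and H7 in the Region 1 testing order (Protocol 13.5.3.1).

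**Working it through.** **Inputs.** Up to four induction cycles (Protocol 6.1.1) give three between-cycle dosing decisions. At most two reductions are allowed, and a simultaneous etoposide and carboplatin reduction counts as one (Protocol 8.4.5.2; SAP 5.1.2.3). The rules are those of Table 8-5 and Other Toxicities.

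**Overlap within Table 8-5.** Take AST/ALT Grade 2 and normal bilirubin. The bilirubin limb of the first row is met (no change), and so is the AST/ALT limb of the second (reduction). The mirror case, AST/ALT Grade 1 with bilirubin Grade 3, also meets both rows. No precedence is stated.

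**Count after k new Grade 2 AST/ALT episodes, bilirubin up to Grade 2.**

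- Reduction row: min(k, 2), stopping at k = 3.
- No-change row: 0.
- Other Toxicities: max(0, min(k - 1, 2)), stopping at k = 4.

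| Episodes (k) | Table 8-5, reduction row | Table 8-5, no-change row | Other Toxicities |
|---|---|---|---|
| 1 | 1 | 0 | 0 |
| 2 | 2 | 0 | 1 |
| 3 | 2, then stop | 0 | 2 |

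The reduction row runs 1, 2, stop, which reproduces the protocol's ceiling of two. The reduction row and Other Toxicities differ by 1, 1 and 0, so never by more than one. At k = 3 the counts agree but the offset does not: 2 events over 3 cycles (0.67 per cycle) against 2 over 4 (0.50).

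**Enzymes raised at entry.** Suppose AST and ALT are both 4 x ULN at entry and stay there, which is Grade 2 throughout. *Episode* is not defined, so three readings are open:

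- Each cycle is a new episode: 2 reductions by Cycle 3 and a stop before Cycle 4.
- The persistent elevation is one episode: 1 reduction.
- Only drug-related change, or a further increase, counts: 0 reductions.

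**Route into the endpoint.** SAP 5.1.2.3 and 5.2.1.4 derive reductions from administered doses, comparing each cycle with the one before within a 10% window. Sites do not report a count, so any inconsistency enters through the dose given.

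**Scale, as illustration only.** The documents do not give the share of patients affected. Assume 2% to 5%; of the 106 planned patients that is 2.1 to 5.3, or about 2 to 5. For underlying rates, borrow the neutropenia dose reductions in Study G1T28-02 (Protocol 4.3.1): 10/37 = 0.270 on placebo and 2/38 = 0.053 on trilaciclib. These are proportions of patients with one cause of reduction, used here as if they were events per patient. If a share f in each arm gains d reductions, the rate ratio is (0.053 + d f) / (0.270 + d f). With f = 0 it is 0.20.

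| f | d = 1 | d = 2 (extreme case) |
|---|---|---|
| 2% | 0.073/0.290 = 0.25 | 0.093/0.310 = 0.30 |
| 5% | 0.103/0.320 = 0.32 | 0.153/0.370 = 0.41 |

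Protocol 4.3.1 prints 32.4% beside 10/37, which is 27.0%. With 0.324 the starting ratio is 0.16, and for d = 2 it moves to 0.26 (f = 2%) or 0.36 (f = 5%).

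**The case against.** Much can be said for the protocol. If normal bilirubin alone meant no change, Grade 4 AST/ALT with normal bilirubin would also mean no change, and the AST/ALT limb of the second row would rarely decide anything. The natural reading is that either limb of that row triggers a reduction. Other Toxicities follows dedicated hepatic, gastrointestinal and hypersensitivity headings, so it looks like a residual rule. The endpoint is all-cause by design, so hepatic reductions belong in it. H3 is tested only after H1 and H2 succeed.

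This makes the literal no-change reading less likely but does not remove the conflict. The table states no precedence. In Other Toxicities only the Grade 3/4 sentence is limited to toxicities not already covered; the Grade 2 sentence extends to any nonhematologic, chemotherapy-related toxicity except alopecia.

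A reader might infer three stronger points that the documents do not support:

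- **That the protocol penalises enzymes already raised at entry.** Section 8.4.5.2 ties adjustments to drug-related toxicity, and the sentence under the table acts only on a further increase. That sentence can coexist with the table; the gap is that their relation is unstated. Section 6.1.1, which accepts a return to baseline, governs whether a cycle may start and does not set the dose.
- **That identical patients generally yield 0 or 2 events.** A single new episode gives 0 or 1.
- **That the comparison is biased between arms.** Treatment is blinded and randomized 1:1, and nothing shows the readings differing by arm.

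**Conclusion.** The concern holds as a contradiction in the dosing text that feeds a tested endpoint. Table 8-5 overlaps itself, and it differs from the Grade 2 rule in Other Toxicities on the first episode and on when treatment stops (third episode versus fourth occurrence). For enzymes raised at entry the text is ambiguous; it states no rule that plainly requires a reduction.

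The size is 0 versus 1 reduction for one new Grade 2 episode. It reaches 0 versus 2 only with at least two episodes under the no-change reading, or if a stable entry elevation counts as new each cycle. The expected effect on H3 and MAHE is between-site noise, with dilution of the rate ratio if the extra reductions fall equally on both arms. How large that is cannot be known without the frequency, so the scale figures rest wholly on the assumed 2% to 5% and the borrowed rates. The variation in chemotherapy given is reason enough to settle the text.

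**What to change.** Reconcile Table 8-5, the sentence beneath it, the drug-related condition in Protocol 8.4.5.2 and the Grade 2 rule in Other Toxicities, so that every AST/ALT and bilirubin combination leads to one action. State whether Other Toxicities excludes hepatic events, how enzymes already raised at baseline are handled, and what counts as a new episode. Which action applies is for the sponsor's clinicians. Issue the result to all sites. This takes a clarification letter or a minor amendment and no extra visits.

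If induction is already complete, tabulate by arm the reductions that follow a hepatic trigger, separately from the rest. The SAP's dose-reduction derivation describes no reason field, so this needs linkage of the Day 1 chemistry, the action taken recorded for adverse events (Protocol 11.4.1.6) and the dosing pages. The cost is programming time on data already collected.
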